5. The proportion of schools (in the intervention villages) who have at least 70% of surveyed teachers trained in using the tools to track girls in their school
6. The proportion of schools (in the intervention villages) who effectively use the tracking tools for all the girls in their school
7. Proportion of surveyed teachers who report programmes in their school to build leadership among girls
8. Proportion of surveyed teachers who report positive attitudes on gender equality
9. Proportion of surveyed teachers who articulate positive attitudes towards girls completing secondary education.

Families of adolescent SC/ST girls:

1. Changes in gender norms around marriage and education of girls
2. Accessibility and expanded opportunities for girls to enter and continue in formal secondary education
3. Engagement and accountability of families for the education of adolescent girls
4. Awareness on the issues, schemes and options
5. Participation of family members in campaigns and discussions and problem solving
6. Number of families allowing the girls to attend special/ tuition class

7. Utilisation of entitlements / livelihood schemes
8. Understanding of the barriers to girls continuing secondary school and the solutions to those barriers

Communities served by the schools:

1. Change in gender norms around marriage and education of girls
2. Engagement, support and accountability of communities for the education of adolescent girls
3. Accessibility and expanded opportunities for girls to enter and continue formal secondary education
4. Awareness on the issue of school drop outs and its negative outcomes, schemes and option
5. Participation of community members in campaigns and discussions and problem solving
6. Understanding of the barriers and solutions to the issue
7. Vigilance among community groups on girl child marriage and school drop out

Policy impacts

Policy impacts act at the district, state, and national level and are not outcomes compared between arms of the trial but instead measure effects of the trial's impact on the wider policy environment. If the intervention is shown to be effective, policy impacts may include:

1. Government development of policies and guidelines based on this intervention model for scale up
2. Government understanding of why the intervention is important and government support for the intervention in government schools.

Evaluation design

Summary:

Study design

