Demographics	Geographic location, relationship to adolescent girl, age, caste, number of children (male and female), current marital status, education, occupation, land holdings and household income, whether anyone in the family is a Devadasi/sex worker, if yes, relationship to the adolescent girl
Medium-term outcomes	
Accessibility and expanded opportunities to enter and continue formal secondary education	Respondents' perception of the availability and accessibility of secondary school education (cost, infrastructure, transport, distance, school environment, attitudes of teachers/schools) Respondents' perceptions of opportunities to secondary education (extended family support, support from the community/neighbourhood, livelihood and economic opportunities after secondary education)
Engagement and accountability for education of adolescent girls	Support and value for education, engagement with school/neighbourhood/project staff on adolescent girl education, perceived economic/social benefits/burdens of girls' education to the family Number of visits to the school, reason, number of times enquired with daughter on syllabus or performance or school activities, appreciation, allocating time Decision and barriers
Changes in gender norms around education and marriage of girls	Respondents' perception and attitude on relative education and marriage of boys and girls, Number of years a girl and a boy to be educated. Perception about age at marriage of boys and girls, How soon the girls and boys to be get married, Perception about girls roles in household chores in relation to education and in relation to boys
Short-term outcomes	
Aware of issues, schemes and option	Whether aware of girls issues; whether aware of each of the existing government schemes/subsidies to encourage education; whether aware of various options available; whether their girl is currently availing them, reasons for not availing the services
Participation in campaigns and discussions and problems solving	Whether families participate in campaign addressing girls education and marriages; do they discuss the issues; with whom they discuss and how are they solving their problem
Allowing girls to attend special/tuition classes	Whether aware of the special/tuition classes for girls at school; whether their girl is currently availing these services; reasons for not availing; discuss subject matter with girl and tuition teachers;

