Utilization of entitlements/livelihood options	Whether aware of the girls entitlements; whether availing such services; reasons for not availing entitlements/livelihood options
Understanding of the barriers and solutions to the issue	Whether aware of the barriers the girls experience in school drop outs; what are the barriers and solutions; whether their girl child experience similar issues

Survey of schools

The Medium- and short term outcomes among schools will be measured through surveys of schools and teachers in intervention and control sites at baseline and follow-up. All Principals and 2 teachers (1 male and 1 female) per school in each of the 144 schools will be randomly selected from the list and interviewed at the beginning of year 1 and the beginning of year 4, using a questionnaire on the expected medium- and short-term outcomes among schools. In addition 2 SDMC members will be interviewed per school except where one SDMC committee covers 2 schools. In these cases, 2 SDMC members will be interviewed.

Table 6 provides a summary of the different major and sub-domains under each indicator that will be measured among the school principals and SDMC members.

Table 6: Indicator domains and sub-domains that will be measured in surveys of school principals, SDMC members and Teachers

Major domains	Minor domains
Identification details	Geographic location, type of school, aid status, school category, medium of teaching, education type, number of teachers (male and female), facilities and infrastructure, schemes and services available
Medium-term outcomes	
Accessibility and expanded opportunities to enter and continue formal secondary education	
Respondents' perception of the availability and accessibility of secondary school education (cost, infrastructure, transport, distance, school environment, attitudes of teachers/schools)
 
Respondents' perceptions of opportunities to secondary education (support from girls' family, support from the community/neighbourhood, livelihood and economic opportunities after secondary education)

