Improved capacities and accountability to be responsive and facilitate the retention of girls in school	
Whether the school finds it necessary to track the girls for entry, continuity and completion
 
How many girls have been tracked?
 
How has the school improved entry, continuity and completion of secondary school among girls?
 
Does the school have any community outreach activities to facilitate girls' entry and retention in schools?

Short-term outcomes	
Effective tracking of girls in schools	
Whether the school is using any tool to track and monitor school entry, continuity and completion
 
What are the tools, their experiences of using these tools, benefits and challenges; Current mechanisms of tracking, Current number of girls being tracked
 
Does the school conduct parent meetings?, how frequently, does the school contact families of students
 
Did anybody from the school contacted girl/family members regarding girls education, follow-up, discussed girls performance, number of visits

safety and gender equitable environment in schools	Does the school have safety policies for adolescent girls, what are they, what has been their experiences with these policies; whether gender difference exists in safety is concerned
leadership programs for girls	Does the school have leadership programs for adolescent girls, what are they, what has been their experiences with these programs
Understanding of gender issues by	Gender equitable men scale (GEMS)

Qualitative research

Case studies using lifelines will be conducted to investigate how *Sabala* has affected the adolescent girls and their families in addressing school dropout, early marriage, sexual debut and entry into sex work. Additionally, in-depth interviews will be done with girls, parents and various community stakeholders to examine changes in the community, and changes in the levels of appreciation and support from government towards these interventions. Methods are described briefly in terms of the target groups, number, frequency and the general content. All qualitative research will be equally divided between Bijapur and Bagalkot districts, except where otherwise mentioned.

Case studies

[figure not shown]

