At project completion, we will assess whether, at follow up, there are significant differences between the intervention and control girls in the key indicators of entering 8th standard, completing tenth standard, being married, having sexual debut and entering into sex work. In the course of the analysis we will present simple cluster summaries for the primary outcomes. We will perform statistical tests, using the t-statistic, to assess the significance of and differences observed between the arms.

The final analysis will assess whether the intervention and control schools, adolescent girls and their families significantly differ in terms of the intermediate and short-term outcomes. As recommended by Hayes and Moulton²², given the large number of clusters and because of reasons related to statistical efficiency, individual-level regression methods will be used to test for significant differences in outcomes between intervention and control arms. For each outcome of interest (e.g., the proportion of girls married at the end of the study period, the proportion of girls passing to 10th Standard, etc.), multivariable logistic regression models using generalized estimating equations (GEE)^{23,24} to address clustering at the school level will be estimated. Stata 11 will be used for all analyses. Similar methods will be used to compare short- and medium-term outcomes among SC/ST girls and their families between intervention and control arms.

Qualitative data analysis

The qualitative data will be transcribed and translated into English. Qualitative analysis packages (eg., NVivo9, ATLAS TI) will be used to identify key issues and themes emerging over time. These findings will be used along with the quantitative findings to understand the impact of the intervention.

Addressing confounding factors, selection bias, spill over effect and impact heterogeneity

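### The teachers' gender-attitude outcome is fixed as a proportion positive with no cut-off, although the school survey collects a gender scale; analysing the score would usually be more precise

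*Protocol*

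**What the plan says.** Under Process level outcomes, Schools/SDMCs/Teachers, item 8 reads "Proportion of surveyed teachers who report positive attitudes on gender equality". Neither that list nor the rest of the protocol says what score or answer counts as positive.

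Table 6 is headed "Indicator domains and sub-domains that will be measured in surveys of school principals, SDMC members and Teachers". Among its short-term outcomes, in a row on understanding of gender issues, it lists the "Gender equitable men scale (GEMS". The row label is cut off in the available text, so which respondents answer the scale cannot be read there.

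Under Analysis of primary outcomes, the scope of the intermediate and short-term comparison includes schools: "The final analysis will assess whether the intervention and control schools, adolescent girls and their families significantly differ". The text refers in general to individual-level regression, then names "multivariable logistic regression models using generalized estimating equations" for each outcome of interest. Its two examples, being married and passing to 10th standard, are both binary. It adds: "Similar methods will be used to compare short- and medium-term outcomes among SC/ST girls and their families between intervention and control arms".

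**The concern.** A scale is collected, but the outcome is defined as a yes/no share. A later analysis plan that keeps to item 8 can choose the cut but cannot analyse the score. This is therefore a choice the protocol makes, not only a detail it leaves open.

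Two things are at stake. First, dichotomising a graded measure loses precision, and the teacher sample is small to begin with. Second, the result depends on a threshold nobody has stated. Process outcomes exist to explain how the intervention reaches its primary and secondary outcomes, and study question 4 asks about causal pathways, including gender norms. A real shift in teacher attitudes could be missed and that pathway read as inactive.

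**Working it through.** **Check against the protocol's own figures.** No power, effect size, SD, ICC or cut-off is given for the teacher outcome. The nearest stated figures are the cluster counts for the co-primary outcomes. The unmatched Hayes–Bennett formula is

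c = 1 + (1.96 + 0.84)² × [p0(1−p0)/m + p1(1−p1)/m + k²(p0² + p1²)] / (p0 − p1)²

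With p0 = 0.17, p1 = 0.119, m = 28 and k = 0.15, 0.20, 0.25 it gives 30.4, 32.7 and 35.6, as in the transition table. The protocol's conventions are thus two-sided 5% and 80% power, and the same 5% level is used below.

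**Inputs from the protocol.**
- Two teachers per school (Survey of schools).
- 71 intervention and 73 control schools in 80 villages, with the village randomised.
- Teachers: 2 × 71 = 142 and 2 × 73 = 146, total 288, so about 144 per arm and 288/80 = 3.6 per village.

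**Assumed inputs.** Normally distributed score; shift d = 0.35 SD; village ICC 0.05 to 0.20; 50, 70 or 80% of control teachers positive.

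**Score analysis.** Design effect DE = 1 + (3.6 − 1) × ICC, and power = Φ(d / √(2·DE/144) − 1.96).
- ICC 0.05: DE = 1.13, effective n = 144/1.13 = 127.4, SE = √(2/127.4) = 0.125, and 0.35/0.125 − 1.96 ≈ 0.83. Power is 80%.
- ICC 0.20: DE = 1.52, effective n = 94.7, SE = 0.145. Power is 67%.

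**Analysis after a cut.** If a share c of controls is positive, the intervention share is Φ(Φ⁻¹(c) + 0.35): 63.7% for c = 50%, 80.9% for 70%, 88.3% for 80%. The ICC of the binary variable comes from the bivariate normal. For c = 50% it is 0.032 at score ICC 0.05 and 0.128 at 0.20. Power is then that of a two-proportion test at the correspondingly deflated n.

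| Village ICC | Score | 50% positive | 70% positive | 80% positive |
|---|---|---|---|---|
| 0.05 | 79.8% | 61.6% (−18.2) | 54.6% (−25.2) | 46.6% (−33.1) |
| 0.10 | 75.4% | 58.4% (−16.9) | 51.7% (−23.6) | 44.4% (−31.0) |
| 0.20 | 67.3% | 52.8% (−14.5) | 46.8% (−20.6) | 40.3% (−27.0) |

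Losses, in points, are taken before rounding.

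**Sensitivity to the assumed shift** (ICC 0.05, cuts at 50 to 80% positive): the loss is 3 to 4 points at 0.1 SD, 11 to 16 at 0.2 SD, and 9 to 25 at 0.5 SD. At 0.1 SD neither analysis has useful power (12% on the score). If 90% of controls were positive, the loss at about 0.35 SD and ICC 0.05 would be about 47 points.

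**The case against.** Four points can fairly be made for the plan.

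- **The link from GEMS to item 8 is inferred.** The Table 6 row is truncated and speaks of understanding of gender issues, while item 8 speaks of attitudes. The questionnaires are separate documents and are not shown, nor is the scoring of the scale. This stands, and the point is conditional on the link.
- **Scoring and cut-offs are commonly left to an analysis plan.** This holds for the missing cut-off taken alone. It does not answer the wording of item 8, which already sets the form of the outcome as a proportion.
- **The power loss is not a figure of this protocol.** This also stands. It depends on the assumed shift, ICC and control share.
- **Little hangs on one process outcome.** The trial is sized on four binary outcomes in girls, and teachers are also interviewed in depth. This limits the importance of the point but does not remove it.

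A reader might go further and infer that, because logistic GEE is the only regression named, the girls' and families' scores and counts (self-esteem, school visits, absences) must also be cut in two. The documents do not support that. The analysis section speaks generally of individual-level regression and then of similar methods, which leaves room for a GEE with another link. Absences and shifts in attitude are not worded as proportions. Several of the other measures are questionnaire domains, not defined endpoints. The sentence on similar methods names girls and families, so it does not tie teachers to the logistic model either.

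**Conclusion.** The concern holds for item 8: it fixes the teacher gender-attitude outcome as a proportion positive, without a cut-off, where the same survey collects a gender scale. Provided GEMS is the instrument behind it, a score analysis would usually be more precise and would not depend on an unstated threshold.

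For a 0.35 SD shift, village ICC 0.05 to 0.20 and 50 to 80% of controls positive, the cost is about 14 to 33 points of power, from about 67 to 80% on the score. That range should not be quoted without its assumptions, since the loss nearly vanishes for very small shifts. This is a modest improvement to one explanatory outcome. It does not touch the co-primary analyses.

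**What to change.** - Redefine item 8 as the between-arm difference in mean GEMS score at follow-up among surveyed teachers. Estimate it with an identity-link GEE or from village means, accounting for clustering by village, the unit randomised.
- Keep the proportion positive as a descriptive figure, with its cut-off stated in advance.
- Confirm in Table 6 that teachers answer the scale and that it is the source for item 8.
- Under Analysis of primary outcomes, add that the logistic GEE applies to binary outcomes.

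The cost is wording only, with no new data. The one small downside is that a mean difference on a scale is harder to explain to policy makers than a percentage; the descriptive proportion covers that need.

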2. Assess the impact of the intervention on age at marriage, age at sexual debut and age of entry into sex work among adolescent SC/ST girls in schools and communities that have access to the intervention.
3. Explore how the intervention has affected the school and the communities' response to premature high school drop-out by SC/ST girls.
4. Investigate the processes and causal pathways through which positive changes occur in the following areas: support and value for education; self-esteem and confidence among adolescent girls; self-perceived safety and social status among adolescent girls and in their social networks; and culturally prescribed social expectations and gender norms.

Study components

This is a rigorous evaluation study that will be implemented by the Karnataka Health Promotion Trust (KHPT), based in Bangalore, Karnataka, in collaboration with the Social and Mathematical Epidemiology Group, London School of Hygiene and Tropical Medicine (LSHTM), and the Centre for

¹⁷ Standards 8, 9, 10.

Global Public Health, University of Manitoba, Canada. The project uses a cluster randomized, controlled trial (RCT) design, and has three main components:

1. A quantitative assessment involving two sequential cohort studies, one initiated in year 1 and another initiated in year 2, of a sample of SC/ST girls and their families at baseline and following the intervention.
2. A qualitative assessment documenting the process of implementation and change using qualitative methods with:
 - a. SC/ST girls
 - b. Families
 - c. Teachers
 - d. Community leaders
 - e. Policy makers
3. A robust monitoring system to monitor the intervention activities at school and community level.

Outcomes

Adolescent girls

This is a complex intervention which aims to act upon many modalities to affect change for SC/ST girls. For that reason we will be collecting a number of outcomes, many of which will be used to understand the effects observed in the primary and the secondary outcomes.

There are four **co-primary outcomes** on which the trial is sized:

1. Proportion of those enumerated in 7th standard (the study cohorts) who ENTER into grade 8th
2. Proportion of those in the study cohorts who complete 10th standard
3. Proportion of girls in the study cohorts who are married at end line.
4. Proportion of girls in the study cohorts who experienced first sexual intercourse at end line

The **secondary outcomes**:

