SC/ST girls will be enumerated and included in the cohort. We will conduct a complete-capture enumeration of all SC/ST girls in all trial sites, therefore, all SC/ST girls will be approached for inclusion in the trial.

Families

All families of SC/ST girls will be included in the cohort.

Sample size

The sample size calculations are based on the four co-primary outcomes:

1. Percentage of those enumerated in 7th standard (the study cohorts) who ENTER into grade 8th
2. Percentage of those in the study cohorts who complete 10th standard
3. Proportion of girls in the study cohorts who are married at end line.
4. Proportion of girls in the study cohorts who experienced first sexual intercourse at end line

The sample size calculations are based on the parameters shown in the table below. The baseline numbers are found in the KSS Karnataka report for 2010-2011, a rural assessment by KHPT in 2013, the district level household surveys (DLHS) from 2007-2008, and the Integrated Biological and behavioral Assessment (IBBA) conducted by KHPT from 2006-2011. Broadly speaking, the expected effect sizes are guided by the aim of the intervention to bring the outcomes among SC/ST girls in-line with all girls. Therefore, we have used the prevalence of the outcomes in these surveys to estimate plausible effect sizes.

Parameter	Notes
Harmonic mean cluster size	This is based on an enumeration carried out in the 225 high schools located in 121 villages by KHPT. Approximately 15 SC/ST girls are available at each school
Refusal/loss to follow-up	Refusal and loss to follow-up are expected to be low, approximately 5-10% (14 girls per cluster is used in the calculation, multiplied by 2 to account for the two cohorts)
Between cluster variation (k)	The between cluster variation in the outcomes is not known. Therefore, we have reported sample sizes for a range of values.
Control arm proportions	

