
 1. Proportion transitioning 7-8th (actualized in terms of the proportion dropping out between 7th and 8th) 2. Proportion completing 10th (actualized in terms of the proportion dropping out between 7th and 10th) 3. Proportion married at end line 4. Proportion sexual intercourse at endline 	
 1. For this we calculate sample size calculations for a range of drop-out proportions, from 9% (the State level drop-out proportion for SC/ST girls only) and 17% (the dropout rate among all girls in Bijapur district. These are conservative estimates since we expect that the effects of being SC/ST will augment the figure for the study districts (figures from SSA Karnataka report for 2010-2011). 2. The rural assessment in selected villages in Bijapur and Bagalkot districts by KHPT 2013 found drop out of 34% among devdasi girls. We have assumed 30-40% drop out before standard 10. 3. The District Level Household Surveys (DLHS-2007-08) collected data on age at marriage and has a reasonable sample size in each district. About 21% of the women aged 18-25 married before the age of 15 years. A higher percent of SC/ST women were married as compared to others (25.9% against 19.3%). Therefore the proportion is likely to be around 25% 4. Data from the IBBA among FSWs conducted in

the district of Belgaum found 44.77% of the FSWs reported their first sex was before the age of 15 years. Given 25.9% of the SC/ST women married before the age of 15 years, the proportion who had their first sex before 15 years will likely be a number above this, but most likely less than 44.7%. The Polling Booth Surveys conducted in the rural areas of these districts in 2011 found that 8% of the unmarried females (15-24 years) had ever had sex, whereas 5.3% of the married females (15-24 years) had sex before marriage in Bijapur district. Therefore the proportion who had sex before 15 years is likely to be a number above 30%. We have assumed a conservative range from 20-35%.

Effect (risk ratio)

The risk ratios are guided by comparisons between the estimates of the outcomes in the SC/ST girls and outcome proportions in all girls.

1. Proportion transitioning 7-8th
2. Proportion completing 10th
3. Proportion married at end line
4. Proportion sexual intercourse at endline

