1-type I	Power	Control p	Cluster Size	% reduction	Intervention p	K	# clusters per arm
0.95	0.80	17%	28	30%	11.9%	0.15	30.4
						0.20	32.7
						0.25	35.6
						0.15	24.9
						0.20	26.7
						0.25	29.1
		33%		11.4%	0.15	40.0	
					0.20	42.3	
					0.25	45.2	
					0.15	32.7	
					0.20	34.5	
					0.25	36.9	
9%	5.9%	35%	28	35%	5.9%	0.15	41.7
						0.20	43.3

¹⁹ Hayes RJ and Bennett S, Simple sample size calculation for cluster-randomized trials, International Journal of Epidemiology, 1999; 28, 319-326

			45.4
		0.25	
			31.3
40%	5.4%	0.15	
			32.4
		0.20	
			33.9
		0.25	

Retention in school

We have reported a range of Risk Ratio minimum detectable effect sizes of RR=0.75-0.70. The lower effect size than for outcome 1 reflects the perception that this will be harder to influence with the intervention as the barriers to staying in school increase over time.

The *Sarva Shiksha Abhiyan Karnataka Analytical report 2010-11* (Education in Karnataka 2010-11) shows a higher dropout rate of SC/ST girls (22.5%) in transition from standard 8 to standard 10 compared to all girls (16.5%) in the state: this transition is an important stage in ensuring retention until the end of standard 10 and is how the 'retention' outcome will be actualized. The minimum detectable effect sizes of RR=0.75-0.70 are assumed on the basis that the intervention aims to bring retention of SC/ST girls in line with with the state average among all girls. The ratio between SC/ST girls and all girls of the dropout rates during transition from standard 8 to standard 10 is 0.73. This ratio is used as a indicator for the plausible effect of the intervention on retention to standard 10.

1-type I	Power	Control p	Cluster Size	% reduction	Intervention p	K	# clusters per arm			
0.95	0.80	40%	28	20%	32.0%	0.15	28.3			
						0.20	33.9			
						0.25	41.2			
		23%		30.8%	0.15	21.3				
					0.20	25.5				
					0.25	30.8				
		0.95		0.80	30%	28	20%	24.0%	0.15	38.8
									0.20	44.4
									0.25	51.7
23%	23.1%		0.15		29.1					
			0.20		33.3					
			0.25		38.6					
0.95	0.80		20%		28		23%	15.4%	0.15	44.8
									0.20	48.9
									0.25	54.2
		25%	15.0%	0.15		37.7				
				0.20		41.1				
				0.25		45.5				

Proportion married before age 15

The intervention will target marriage directly through school and home based interventions. Therefore, we aim to decrease the proportion married before 15 by 25-30%, corresponding to risk ratios of RR=0.75-0.70.

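### Co-primary outcome 2 is defined from two different starting grades, and the retention text gives a risk-ratio range that its own table does not use

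*Protocol*

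**What the plan says.** The Outcomes section gives the first co-primary outcome as "Proportion of those enumerated in 7th standard (the study cohorts) who ENTER into grade 8th" and the second as "Proportion of those in the study cohorts who complete 10th standard". The first item ties the study cohorts to girls enumerated in 7th standard. The Sample size section repeats the second outcome as "Percentage of those in the study cohorts who complete 10th standard".

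Two operational definitions of the second outcome follow:

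- **Sample size, control-arm proportions:** "Proportion completing 10th (actualized in terms of the proportion dropping out between 7th and 10th", with the assumption "We have assumed 30-40% drop out before standard 10".
- **Retention in school:** after quoting 22.5% drop-out for SC/ST girls and 16.5% for all girls between standards 8 and 10, it says "this transition is an important stage in ensuring retention until the end of standard 10 and is how the 'retention' outcome will be actualized".

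On effect size, Retention in school says "We have reported a range of Risk Ratio minimum detectable effect sizes of RR=0.75-0.70" and later "The minimum detectable effect sizes of RR=0.75-0.70 are assumed on the basis". Its table has reductions of 20% and 23% at 40% and 30% control drop-out, and 23% and 25% at 20% control drop-out. The effect row of the parameter table gives 20-25%, the section on K uses 20%, 23% and 25%, and the summary of the sample-size results concludes on 25%.

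**The concern.** The two definitions start from different grades, so they can cover different girls and give different results. Whoever writes the analysis could follow either one with the Protocol's support.

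The 8th-to-10th version states no denominator. The natural reading is girls who entered 8th, although the Protocol does not state a plan to restrict the analysis to them. On that reading, the analysis would condition on something that happens after randomisation and is itself the first co-primary outcome. Girls whom the intervention brings into 8th would join the intervention-arm denominator without a counterpart among controls, and the gain made at 7th-to-8th would not count.

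The bias has no fixed direction. If the intervention works only after entry, the all-enumerated version shows the smaller effect. That is why the choice should be fixed before outcome data are seen.

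The risk-ratio misstatement is a smaller matter. It tells the reader that the trial was sized for a larger effect than the table used.

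**Working it through.** **1. Reproducing the retention table.** The Protocol cites the Hayes and Bennett method for an unpaired t-test. Clusters per arm are

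c = 1 + (z₀.₉₇₅ + z₀.₈₀)² × [p₀(1−p₀)/m + p₁(1−p₁)/m + K²(p₀² + p₁²)] / (p₀ − p₁)²

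with m = 28 and 80% power. The 5% level is taken as two-sided; the Protocol does not say, but this reproduces its figures. For p₀ = 0.30, a 23% reduction (p₁ = 0.231) and K = 0.20: 1 + 7.849 × (0.00750 + 0.00634 + 0.00573)/0.004761 = 33.3, as printed. All 18 cells reproduce to rounding with the 20%, 23% and 25% reductions shown. The table's arithmetic is therefore right and its range is RR 0.80-0.75. No cell uses RR 0.70.

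**2. What the misstated range would imply.** At 30% control drop-out and 28 girls per cluster:

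| Reduction | K = 0.15 | K = 0.20 | K = 0.25 |
|---|---|---|---|
| 20% (table) | 38.8 | 44.4 | 51.7 |
| 23% (table) | 29.1 | 33.3 | 38.6 |
| 25% (prose, RR 0.75) | 24.6 | 28.0 | 32.4 |
| 30% (prose, RR 0.70) | 16.9 | 19.2 | 22.1 |

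The prose range needs 17-32 clusters per arm; the table's reductions need 29-52.

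**3. Which definition fits the 30-40% assumption.** Take 9-17% non-entry (control-arm proportions) followed by 22.5% later drop-out (Retention in school). Drop-out from 7th to 10th is n + (1−n) × 0.225, which is 29.5% at n = 9%, 32.6% at 13% and 35.7% at 17%. This agrees with 30-40%; 22.5% does not.

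**4. How far the two versions can differ.** Let n = 0.13 (control proportion for transition in the section on K), e = 0.33n the extra entrants (33% reduction), c = 0.225, r the post-entry reduction, and d the drop-out among extra entrants. The Protocol gives no value for d, so 22.5-80% is an assumed range.

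- Entrants-only RR = {[(1−n)c(1−r) + e·d]/(1−n+e)}/c
- All-enumerated RR = [(n−e) + (1−n)c(1−r) + e·d]/[n + (1−n)c]

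Where r also applies to extra entrants, d becomes d(1−r).

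| Scenario | Entrants only | All enumerated |
|---|---|---|
| Transition effect, r = 0, d = 22.5% to 80% | 1.00 to 1.12 | 0.90 to 0.97 |
| Transition effect, r = 0.25 except in extra entrants, d = 22.5% to 80% | 0.76 to 0.88 | 0.75 to 0.82 |
| Transition effect, r = 0.25 in all entrants, d = 22.5% to 80% | 0.75 to 0.84 | 0.74 to 0.80 |
| No transition effect, r = 0.25, n = 9% to 17% | 0.75 | 0.83 to 0.87 |

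**5. Power with 40 clusters per arm, 25% reduction.** Solving the same formula for power:

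| Control drop-out, girls per cluster | K = 0.15 | K = 0.20 | K = 0.25 |
|---|---|---|---|
| 30%, 28 | 95.0% | 92.0% | 87.7% |
| 22.5%, 28 | 86.8% | 83.3% | 78.9% |
| 22.5%, 24.4 (28 × 0.87, non-entrants removed) | 82.6% | 79.2% | 74.9% |

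For a 23% reduction at K = 0.20, moving from 30% to 22.5% control drop-out raises the requirement from 33.3 to 43.7 clusters per arm, above the 40 planned.

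**The case against.** The strongest defence is that the outcome is not split where outcomes are defined. The Outcomes section, the list at the head of Sample size and Analysis of primary outcomes all speak of completing 10th standard. The 8th-to-10th clause sits in a paragraph justifying an effect size, calls the transition a stage, and ends by using the 0.73 ratio as an indicator of a plausible effect. No text plans to drop non-entrants. This limits the weight of the point but does not remove it: the clause says how the outcome will be measured, and it conflicts with the parameter table on the starting grade.

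The size of the harm is also contestable. Drop-out of 40-80% among extra entrants is nowhere in the Protocol. At 22.5%, with effects at both stages, the versions almost agree (0.75 against 0.74, or 0.76 against 0.75). With d held at 22.5%, a clear gap needs an effect at only one stage: 1.00 against 0.90, or 0.75 against 0.83-0.87. That is fair, and these are the figures to rely on.

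Three smaller objections stand in part:

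- The 28 girls per cluster are used for every outcome, so they say little about this denominator. The 20% control block also lies outside the assumed 30-40% and close to 22.5%.
- The 30% comparator is weakly sourced. The parameter table leans on 34% among devadasi girls, while the literature section describes a 34% figure as drop-out by age 10. The chained 29-36% in step 3 supports 30% without that source.
- The risk-ratio error alone is editorial. The table used the smaller effects, and RR 0.75 lies in both ranges. No cluster count rests on 0.70: the 40 per arm are 34 plus 6 added for contamination.

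**Conclusion.** Both points hold. The Protocol fixes a co-primary outcome in two incompatible ways, and this should be corrected before analysis. The all-enumerated, 7th-to-10th definition is the one that agrees with the outcome lists and the 30-40% assumption.

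The consequence depends on the entrants-only reading, which is plausible but not stated. With extra-entrant drop-out assumed at 22.5%, the reading could turn a risk ratio of 0.90 into 1.00 when only transition improves. If only post-entry retention improves, it gives 0.75 in place of 0.83-0.87. Power for a 25% reduction would be 79-87% in place of 88-95%, or 75-83% with non-entrants also removed. These power figures take the state-level 22.5% as the control proportion and K between 0.15 and 0.25.

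The range RR 0.75-0.70 is an error in the prose; the table is correct.

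**What to change.** 1. In Retention in school, replace the 8th-to-10th operational definition with: did not complete 10th standard, among all girls enumerated in 7th standard, counting those who never entered 8th as not completing. Keep 22.5%, 16.5% and the 0.73 ratio only as a benchmark for the effect size.
2. In the same section, change both statements of RR 0.75-0.70 to RR 0.80-0.75.
3. Optionally, in Analysis of primary outcomes, change the example about passing to 10th standard to completing 10th standard, and add a sentence on why the retention table includes a 20% control block.

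The cost is a few wording changes. Data collection and the table's cluster counts stay as they are.
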